**Table 2 Variables collected per cohort**

Variable	Cohort 1 Mepolizumab- exposed	Cohort 2 Asthmatic comparison	Cohort 3 Non-Asthmatic comparison
Maternal Interviews			
Exposure timing 	√	√	√
Dose 	√	√	√
Duration of medications 	√	√	√
Confounders/effect modifiers	√	√	√
Disease severity (ACT & asthma treatment regimen)	√	√	X
Asthma related hospitalizations and physician visits	√	√	X
Pregnancy outcome	√	√	√
Birth defects	√	√	√
Pregnancy complications	√	√	√
Infant complications	√	√	√
Infant size	√	√	√
Medical Record Abstraction			
Pregnancy validation	√	√	√
Pregnancy outcome validation	√	√	√
Exposure timing validation 	√	√	√
Dose validation 	√	√	√
Self-reported	√	√	√

Variable	Cohort 1 Mepolizumab- exposed	Cohort 2 Asthmatic comparison	Cohort 3 Non-Asthmatic comparison
prescription validation 			
Major birth defects 	√	√	√

For cohort 1& 2 primarily asthma medication will be assessed.

Information will be dependent on the completeness of the medical record

Performed periodically and before each annual and final study reports

## 8.5. Study size

The proposed sample sizes in each of the three study groups are as follows:

- 200 women exposed to mepolizumab at any time 8 weeks prior to 1st day of last menstrual period and throughout pregnancy
- 300 women with asthma, unexposed to mepolizumab, aiming to represent the full spectrum of asthma severity with emphasis on severe patients
- 300 non-asthmatic controls

**Table 3 Risk and safety estimates for mepolizumab-exposed pregnancies relative to the primary comparison group for selected outcomes available from the cohort arm PPD after 4 years of enrollment and collection of outcomes at birth; all estimates use an  $\alpha$ -level of 0.05.\***

Outcome	No. Exposed N = 200	No. Unexposed Asthmatic N = 300	Risk**	Safety***
All major birth defects	180	270	3.0	2.8
Preterm birth	180	270	2.2	2.0
SGA infant	180	270	1.9	1.8

\*Sample size for all outcomes shown in the table based on 90% of enrolled pregnancies ending in live birth with completed outcome; sample size for all birth defects based on prevalence of 3% in the asthmatic comparison group; sample size for preterm birth based on prevalence of 7% in the asthmatic comparison group (Bakhireva et al, 2008); sample size for small for gestational age infants (SGA) based on prevalence of 10% in the asthmatic comparison group. Power calculations performed in OpenEpi software.

\*\* Minimum RR detectable with 80% power.

\*\*\*Upper 95 % confidence bound for RR=1.

The sample size is considered plausible based on the experience of the PPD research group with previous studies of asthma in pregnancy, but plausibility for the current study is unknown. Although it is unknown to what extent mepolizumab will be used by pregnant women, experience with recruitment in the omalizumab (Xolair) registry provides some support for the proposed sample size. In six years of recruitment, the EXPECT (omalizumab) registry recruited 191 exposed pregnancies (Namazy et al, 2015).

It is expected, based on experience with the EXPECT registry for omalizumab that virtually all mepolizumab-exposed participants will have exposure sometime in the first trimester and will typically enroll in the study upon recognition of pregnancy making the entire cohort analysable for the primary outcome and all secondary outcomes. It is possible that some participants in all three cohorts will enroll after 20 weeks' gestation and therefore will not be included in the analysis of spontaneous abortion.

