Other methods of raising awareness about the study are meeting exhibits at professional practice meetings nationally, regionally and locally, direct mail to health care providers, media, social media, and website. Because treatment with mepolizumb will require expertise in treating severe asthma for administration, these health care providers will be a particular focus of awareness activities. With the assistance of the American Academy of Allergy, Asthma and Immunology, providers who treat women with more severe asthma will be a priority target for awareness.

Women who are interested in hearing more about the study will be referred to or will self-refer themselves to the PPD [REDACTED] for more information. Referrals may be by the woman's HCP or by the PPD [REDACTED] service that the woman contacts directly. Those women who are interested and meet the study criteria as described in Section 8.1 will be invited to enroll. Women who agree to enroll will complete the oral consent process over the telephone, and will then complete the initial telephone interview. Depending on the gestational timing of enrollment, subsequent telephone interviews will be conducted according to the Schedule shown in Table 5 Section 8.7.3. Follow up interviews will be conducted by telephone, and medical records for both the women and infant will be obtained and abstracted for information to validate exposures and outcomes.

The study population by definition consists of volunteers; however, they are expected to represent a wide variety of maternal age, race/ethnic background, and health status (Chambers et al, 2013; Chambers et al, 2010; Bakhireva et al, 2008; Chambers et al, 1996). The participants will reside anywhere in the U.S. or Canada. By definition, the study participants are all female, as this is a pregnancy study. The age of participants is expected to be between 18 and 45; however, women under the age of 18 may enroll with parent/guardian consent, and women over the age of 45 may also enroll.

Upon initiation of recruitment, the study is expected to continue recruitment for five years. Infant follow-up will continue for one year after the last live birth following recruitment of the last subject.

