*Statistical methods*: Descriptive tables will be prepared for characteristics of each of the cohorts in each interim and final report displaying means and standard deviations, or proportions and percentages.

For the primary endpoint of major structural defects and for the secondary endpoint of small for gestational age infants, crude comparisons will be made using exact methods to develop relative risk estimates and their 95% confidence intervals.

For the secondary endpoints of preterm delivery, spontaneous abortion, and stillbirth, survival methods will be used (Kaplan Meier) to estimate crude rates and confidence intervals accounting for gestational timing of enrollment in the study.

Adjusted analyses producing rates and 95% confidence intervals, where numbers permit, will be conducted for major birth defects and small for gestational age infants using logistic regression. Adjusted analyses producing rates and 95% confidence intervals, for preterm delivery, spontaneous abortion and stillbirth, where numbers permit, will be conducted using Cox Proportional Hazards. A minimum of 30 events in the overall analysis sample is required for adjusted analysis for those outcomes assessed with logistic

regression. A minimum of 20 events in the overall analysis sample is required for adjusted analysis for those outcomes assessed with Cox Proportional Hazards.

Confounders will be considered for each adjusted analysis separately, using the method of change in estimate of the effect of exposure to mepolizumab by 10% or more. If one confounder is identified, direct adjustment will be performed. However, given the expected low frequency of events in a study of this size, if two or more confounders are identified in any given analysis, a propensity score approach for adjustment will be considered.

Appropriateness of models will be assessed graphically and by standard statistical methods

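### Table 3 dates its power and precision figures to 4 years of enrolment, against a 5-year accrual plan, and its primary-endpoint row is slightly too favourable even at the stated 180/270 pregnancies

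*Protocol*

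**What the plan says.** Section 8.5 of the protocol sets targets of 200 mepolizumab-exposed women and 300 women with treated asthma. Table 3 heads its columns with those totals and lists 180 and 270 pregnancies in every row. The footnote gives the reason: "Sample size for all outcomes shown in the table based on 90% of enrolled pregnancies ending in live birth with completed outcome".

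For all major birth defects, the primary endpoint, the table prints 3.0 under Risk and 2.8 under Safety. Risk is defined as "Minimum RR detectable with 80% power". Safety is the upper 95% confidence bound when the RR is 1. The comparator rate is given as "sample size for all birth defects based on prevalence of 3% in the asthmatic comparison group". Alpha is 0.05 with no sidedness stated. OpenEpi is named as the software, without a formula.

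The table title says the figures apply "after 4 years of enrollment and collection of outcomes at birth". Section 8.2 says "the study is expected to continue recruitment for five years", section 8.9.1 repeats the five years, and Table 1 spreads recruitment over Years 1 to 5.

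For the crude analysis of major birth defects, section 8.7.1 states that "crude comparisons will be made using exact methods to develop relative risk estimates and their 95% confidence intervals".

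**The concern.** There are two separate problems. First, the title of Table 3 attaches the figures to a time point at which, on the protocol's own recruitment timetable, the stated numbers will not have been reached. Second, the primary-endpoint row looks a little better than its stated inputs allow, even once enrolment is complete.

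Table 3 holds the only power and precision figures in the protocol. In a pregnancy safety study the bound at RR = 1 tells regulators and prescribers how large a risk a null result could exclude. If it is too favourable, or claimed a year early, a null finding will be read as more reassuring than it is. Because neither the formula nor the sidedness is stated, a reader cannot settle the matter from the table.

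**Working it through.** **Inputs.** Comparator risk p0 = 0.03, alpha 0.05, 80% power, 180/270 analysable (all Table 3 and its footnotes); annual accrual (Table 1). Assumption: two-sided alpha, z = 1.96.

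**Accrual at year 4.**
- Exposed: 20 + 40 + 55 + 55 = 170. Treated asthma: 30 + 60 + 83 + 83 = 256.
- Year 5 adds 30 and 44, giving 200 and 300.
- At 90%: 0.9 × 170 = 153; 0.9 × 256 = 230.4, about 230.

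**Power at RR 3.0 with 180/270** (p1 = 0.09, difference d = 0.06).
- Pooled risk = (180 × 0.09 + 270 × 0.03)/450 = 0.054.
- Null SE: s0 = √[0.054 × 0.946 × (1/180 + 1/270)] = 0.02175.
- Alternative SE: s1 = √[0.09 × 0.91/180 + 0.03 × 0.97/270] = 0.02372.
- Kelsey form (pooled variance under both hypotheses): Φ(0.06/0.02175 − 1.96) = Φ(0.80) = 78.8%.
- Pooled-null form: Φ[(0.06 − 1.96 × 0.02175)/0.02372] = Φ(0.73) = 76.8%.
- Fisher's exact test, enumerating all tables: 75.4%.

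**Reproducing the Risk column at 180/270.** Solving each formula for 80% power:

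| Outcome (comparator risk) | Printed | Kelsey | Pooled-null |
|---|---|---|---|
| Major birth defects (3%) | 3.0 | 3.04 | 3.11 |
| Preterm birth (7%) | 2.2 | 2.17 | 2.19 |
| SGA (10%) | 1.9 | 1.93 | 1.94 |

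Kelsey rounds to all three printed values. The pooled-null form rounds to the printed preterm and SGA values and misses only the primary endpoint, at 3.1.

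**Safety bound for major birth defects.** With risk p0 in both groups, the log-RR upper limit is exp{1.96 × √[((1 − p0)/p0)(1/n1 + 1/n0)]}.
- 180/270: √[(0.97/0.03)(1/180 + 1/270)] = 0.547; exp(1.96 × 0.547) = 2.92. Printed: 2.8.
- Whole-number counts do reach 2.8, but only by moving an input. Counts of 6/180 and 9/270 give RR 1 and a limit of 2.76, at a risk of 3.33%. Counts of 5/180 and 8/270 give 2.82, but the RR is 0.94.

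**The primary-endpoint row at 3%:**

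| Quantity | Printed | 180/270 (full enrolment) | 153/230 (year 4) |
|---|---|---|---|
| Power at RR 3.0, Kelsey | 80% | 78.8% | 72.1% |
| Power at RR 3.0, pooled-null | 80% | 76.8% | 70.4% |
| Power at RR 3.0, Fisher | 80% | 75.4% | 67.3% |
| Minimum RR for 80%, Kelsey to pooled-null | 3.0 | 3.04 to 3.11 | 3.26 to 3.35 |
| Upper bound at RR = 1 | 2.8 | 2.92 | 3.20 |

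**The case against.** The strongest defence is that the row is a matter of formula and rounding. OpenEpi is named without a formula, and the Kelsey form at 180/270 rounds to the whole printed Risk column. Counts entered as whole numbers reproduce 2.8. Planning on a normal approximation for an exact analysis is common, and section 8.9 already concedes limited power for rare outcomes. On timing, the column heads are the full 200 and 300, no passage schedules the primary analysis at year 4, and the final report follows the end of data collection.

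Much of this stands. The 3.0 is defensible as a rounded 3.04, and the SGA entry of 1.9 needs no change, since 1.93 and 1.94 both round to it. The 2.8 is harder to defend, because the counts that produce it depart from either the stated 3% or the stated RR of 1. The conflict over years also remains whatever formula was used.

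Three stronger readings are tempting and not supported.
- **The row was computed on all 200/300 enrolled.** The pooled-null form there does give 2.97 and 2.77. But 200/300 fails elsewhere: with the same formulas the preterm row becomes 2.12 and 1.92 (printed 2.2 and 2.0), and the SGA bound becomes 1.71 (printed 1.8).
- **The table mixes denominators.** This would need the first reading to be proved for the primary row. It is not, because 180/270 can also yield the printed values there.
- **The 4-year title lowers the study's final power.** It does not. 180/270 is 90% of the full five-year enrolment. The year-4 figures describe what the title claims, not the planned final analysis.

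**Conclusion.** The timing contradiction is plain and rests only on the protocol's own numbers. With year-4 accrual and the stated 90%, none of the methods above gives 3.0 or 2.8: power at RR 3.0 is about 70–72% (67% by Fisher's test), the minimum RR is about 3.3 and the bound is 3.2.

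At full enrolment the primary-endpoint row is mildly favourable. The bound is 2.9 rather than 2.8. Power at RR 3.0 is 77–79% by the two normal formulas and about 75% by Fisher's test, so the shortfall is roughly 1 to 5 percentage points. The Fisher figure is relevant because the planned crude comparison is exact.

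These results assume a two-sided alpha and, for the bound, a log-RR interval on expected counts. Kelsey, pooled-null and Fisher are candidate methods, because the protocol does not say which was used. The design and sample size are not called into question by this point.

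**What to change.** - In the Table 3 title, change 4 years to 5 years so that it agrees with Table 1 and sections 8.2 and 8.9.1. Alternatively, keep 4 years and print the figures for about 153/230.
- Restate the safety bound for major birth defects as 2.9.
- Restate its minimum detectable RR as about 3.0–3.1 (3.04 by Kelsey, 3.11 by the pooled-null formula), naming the formula used and stating that alpha is two-sided.
- Add a note that power at RR 3.0 with 180/270 is about 75% under an exact test.
- Leave the SGA row as it is.

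This is a text correction. The cost is that the stated figures become slightly less favourable.

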## 8.6. Data management

Maternal interviews are conducted at enrolment and in each trimester thereafter, depending on the gestational age at which the mother enrolls. An additional outcome interview is conducted by telephone after the end of pregnancy, typically this occurs within 6 weeks but could be up to one year after . These interviews are conducted by telephone and typically take between 30 minutes and 1 hour to complete. The interviews are semistructured and follow interview data collection forms to ensure that all study questions are addressed. Data from each interview form is entered into the study database at the end of the interview by the same person who conducted the interview. Medical records are requested from the hospital of delivery (maternal and neonatal information), obstetric provider (maternal information), paediatrician (neonatal/infant) and any specialty physician (maternal and neonatal/infant information) . When records are

received and catalogued, data is abstracted by trained personnel from each record using a standard abstraction form and entered into the study database. Hard copies of all study forms and medical records are retained in the PPD [REDACTED] at the PPD [REDACTED] PPD [REDACTED]. Several logic checks are built into the study database. In addition, all data entry is validated for a series of predefined critical variables and a random subset are validated for non-critical variables. Access to the database is controlled by password with administrative level access required for certain operations. Hard copies of patient files and subject signed consent forms will be kept in locked file rooms and/or locked cabinets under the supervision of the study investigators.

### **8.6.1. Data handling conventions**

Major birth defects are classified using the CDC coding manual (<http://www.cdc.gov/ncbddd/birthdefects/documents/MACDPcode0807.pdf>) by the Study Manager. All defect classifications are reviewed by co-Investigators. All prenatal exposures to medications and vaccines are coded using the Slone Drug Dictionary (<http://sites.bu.edu/slone-drug-dictionary/>).

Twins or higher order multiples are handled as one pregnancy outcome. For example, if the pregnancy ends in at least one live born infant, the outcome is considered a live born outcome. If either or both twins have a major birth defect, the outcome is considered one major birth defect outcome. Twins are excluded from analyses of preterm delivery and small for gestational age infants.

Lost-to-follow-up status is designated if a participant withdraws from the study, or if the study staff are unable to make contact with the study participant within 12 months of the estimated end of pregnancy in order to obtain outcome information.

**Table 4 Denominators by Outcome**

Outcome	Denominator
Major Birth Defects Among Live Births	Pregnancies ending in live birth; with exposure in 1 st trimester for mepolizumab cohort, and other comparison groups at least one malformed infant in an individual pregnancy is considered one malformed outcome
Major Birth Defects Among All Pregnancies	Pregnancies with any outcome excluding those lost-to-follow-up; with exposure in 1 st trimester for mepolizumab cohort, and other comparison groups; at least one malformed fetuses/infants in an individual pregnancy is considered one malformed outcome
Spontaneous Abortion	Pregnancies enrolled in the study prior to 20 weeks' gestation with at least 1 follow-up data collection point after enrollment date. Exposure can occur any time in pregnancy prior to event.
Preterm Delivery	Pregnancies enrolled prior to 37 weeks gestation and ending in at least one live born infant; excluding twins or higher order multiples due to inherent higher risk of preterm birth in multiples. Exposure can occur any time in pregnancy prior to event.
Small for Gestational Age Infants	Pregnancies ending in at least one live born infant; excluding twins or higher order multiples due to the inherent higher risk of reduced birth size in multiples. Exposure can occur any time in pregnancy prior to event.
Still Birth	All pregnancies, excluding lost-to-follow-up. Exposure can occur any time in pregnancy prior to event.

Coding of outcomes is performed by the study staff using the definitions provided in the protocol. The primary source of information on exposure and outcome is the participant. Validation of study outcomes is performed using medical records. In the case of discrepancies in the two sources of report, the participant is recontacted to determine if the discrepancy can be resolved, and an SOP for adjudicating these decisions has been developed.

Missing values for the critical data for PPD studies are typically very few and nearly always less than 10%. There is generally no need to include imputation strategies; however, depending on the prevalence of missingness, sensitivity analyses will be conducted. These will be documented in the DAP.

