### 8.3. Variables

#### 8.3.1. Exposure definitions

*Mepolizumab-exposed cohort:* Exposure is defined as any dose of mepolizumab for any length of time from 8 weeks prior to the first day of the last menstrual period (LMP) through the end of pregnancy, as reported by the mother and validated through medical record review. The 8 week cut-off prior to LMP is based upon the terminal half life of mepolizumab of approximately 20 days (clearance of mepolizumab is based on five half-lives).

Exposure is defined as yes/no in the first trimester of pregnancy for major birth defects as the primary outcome. For this study, first trimester exposure is defined as any dose between eight weeks prior to 1st day of last menstrual period and 13 weeks after 1st day of last menstrual period. However, exposure to mepolizumab in the second (>13 weeks through 26 weeks after 1st day of last menstrual period) and third trimester (>26 weeks after 1st day of last menstrual period) will be considered for those selected major birth defects that are potentially biologically plausibly related to later pregnancy exposures, e.g., craniosynostosis. For spontaneous abortion, the exposure is defined as yes/no in the first 20 weeks' of gestation, and for the other secondary outcomes, exposure is defined as yes/no anytime in pregnancy.

Gestational age is determined by an algorithm using best available information. If the first day of last menstrual period and cycle length is known, and ultrasound measures of dating are not discrepant according to standard conventions depending on the timing of the ultrasound, the menstrual period dating will be used to calculate gestational age. If the menstrual period dating is uncertain or unknown, and an ultrasound is available, the earliest (and therefore more precise) available ultrasound dating will be used. In the event of absence of any information on dating, the delivery record best estimate of gestational age will be used.

In exploratory analyses, duration of mepolizumab use in pregnancy, specific gestational timing, and dose of mepolizumab will be explored. In the asthmatic comparison group, duration of other asthma medications duration use in pregnancy, specific gestational timing, and doses will be explored.

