### **8.3.2. Outcome definitions**

*Major Birth Defects:* a major structural defect is defined and classified using the CDC coding manual (<http://www.cdc.gov/ncbddd/birthdefects/documents/MACDPcode0807.pdf>), reported by the mother and validated through the medical record. The CDC coding manual is utilized to classify defects reported through the ongoing population-based Metropolitan Atlanta Congenital Defects Program (MACDP) and is based on agreed-upon criteria by CDC investigators for major structural defects regardless of etiology. Infant medical records are abstracted and reviewed by the study research team leaders. Final validation of the classification of all major birth defects reported in the study will be conducted by a VAMPSS Investigator with expertise in the diagnosis of birth defects.

*Preterm Delivery:* preterm delivery is defined as a spontaneous or induced delivery at <37 gestational weeks, reported by the mother and validated through the medical record. Please refer to Section 8.3.1 for further description of the method for defining gestational age and therefore preterm birth.

*Small for Gestational Age (SGA) Infants:* Live born infants who are  $\leq 10^{\text{th}}$  centile on birth weight for infant sex and gestational age will be considered small for gestational age.

The U.S. Centers for Disease Control and Prevention (NCHS) growth charts will be used for full term infants, and the Britton growth charts will be used for preterm infants (Britton et al, 1993). The outcome of birthweight is reported by the mother and validated through the medical record.

*Spontaneous Abortion:* Spontaneous abortion is defined as spontaneous pregnancy loss prior to 20 weeks' gestation. In this study, since women enrol after recognition of pregnancy, spontaneous abortions are only identified after enrollment in clinically recognized pregnancies. This outcome is reported by the mother and validated through the medical record.

*Stillbirth:* Stillbirth is defined as a fetal death that occurs >20 weeks' gestation. This outcome is reported by the mother and validated through the medical record.

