## 8.9. Limitations of the research methods

Potential limitations of the research methods are as follows:

The study relies on a volunteer sample which may or may not be entirely representative of all women who take mepolizumab during pregnancy. However, for a new product used for a relatively rare condition this is likely one of the only methods of obtaining safety information for pregnancy exposures because of the ability to target key patient and provider groups, particularly physicians who treat patients with more severe asthma, to increase awareness about the study.

It is unknown what the distribution of timing of exposure will be in the mepolizumab-exposed cohort. In the EXPECT registry for omalizumab, pregnancy exposures were predominately limited to the first trimester (Namazy et al, 2015). Therefore, it is possible that the study will only be able to address the risks or safety of exposures that occur in the first four to six weeks of pregnancy before women typically recognize that they are pregnant.

The sample size that is achievable for a new product used for a relatively rare condition limits the power to detect differences, especially for rare outcomes such as major birth defects. The study will also be limited in ability to address increased risks for spontaneous abortion as the highest risk for spontaneous abortion occurs in the gestational weeks prior to when women would typically enroll in the study. However, based on expected gestational timing of enrolment, spontaneous abortion rates in late first trimester and early second trimester will be analyzable.

Strengths of the study design are the ability to build on the referral network of PPD [redacted] member services across the U.S. and Canada to identify mepolizumab-exposed pregnancies as well as appropriate comparison group pregnancies, the PPD [redacted] research groups' track record of excellent subject retention (<5% lost to follow-up). In addition,

the study design allows for appropriate comparison to a treated disease group, and for appropriate attention to confounding or effect modification.

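### A fetal death at exactly 20 weeks falls in no endpoint, and stillbirth drops pregnancies lost to follow-up although it is analysed by survival methods

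*Protocol*

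**What the plan says.** **Boundary.** Section 8.3.2 states "Spontaneous abortion is defined as spontaneous pregnancy loss prior to 20 weeks' gestation" and "Stillbirth is defined as a fetal death that occurs >20 weeks' gestation". The text after Table 4 has study staff code outcomes from the protocol's own definitions.

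**Loss to follow-up.** Section 8.7.1 assigns preterm delivery, spontaneous abortion and stillbirth to Kaplan-Meier for crude results and Cox regression for adjusted results. The Still Birth row of Table 4 reads "All pregnancies, excluding lost-to-follow-up". Section 8.6.1 counts as lost any woman who withdraws, and any woman not reached within 12 months of the estimated end of pregnancy. The Spontaneous Abortion row instead asks for enrolment before 20 weeks and at least one data collection point afterwards.

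**Exposure.** Section 8.3.1 says "For spontaneous abortion, the exposure is defined as yes/no in the first 20 weeks' of gestation". The remaining secondary endpoints use the same kind of binary variable, covering the whole pregnancy. Table 4 adds, for spontaneous abortion, preterm delivery, small for gestational age and stillbirth, "Exposure can occur any time in pregnancy prior to event". The survival methods are to "estimate crude rates and confidence intervals accounting for gestational timing of enrollment in the study".

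**The concern.** The two endpoints should together cover every fetal death after enrolment, but the inequalities leave 20 weeks 0 days uncovered. If gestational age is held in completed weeks, all of week 20 is uncovered. Spontaneous abortion and stillbirth are also among the outcomes that section 10 lists for reporting to the sponsor within 24 hours, so a literal reader could hesitate over such a loss there too.

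Survival methods deal with incomplete follow-up by censoring. Excluding a woman because she was later lost selects on the future and discards time during which she was known to be event-free. Two endpoints analysed by the same methods then follow opposite rules, with no reason given.

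On exposure, a fixed yes/no combined with entry at enrolment has one weak spot. A woman first dosed between enrolment and the event must stay event-free up to that dose to be classed as exposed. Counting that interval as exposed pulls the ratio towards apparent safety, which is the unwelcome direction in a safety study.

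**Working it through.** **The plan's own figure.** Preterm birth is the only survival-analysed outcome in Table 3: 180 v 270, control rate 7%, detectable RR 2.2, upper bound 2.0.
- Power at RR 2.2 (15.4% v 7%, two-sided 0.05): the pooled rate is (27.72 + 18.9)/450 = 0.1036, the null SE 0.0293 and the alternative SE 0.0311. Then z = (0.084 - 1.96 × 0.0293)/0.0311 = 0.85, so power is 80.3%.
- Upper bound: exp(1.96 × √(0.93/12.6 + 0.93/18.9)) = 1.99.

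Both reproduce. Table 3 uses simple proportions, so nothing below changes it. The protocol gives no figure for spontaneous abortion or stillbirth.

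**Boundary.**

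| Gestational age at loss | Spontaneous abortion (<20) | Stillbirth (>20) |
|---|---|---|
| 19w6d | yes | no |
| 20w0d | no | no |
| 20w1d, age in days | no | yes |
| 20w1d, completed weeks (= 20) | no | no |

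For scale, at an assumed stillbirth rate of 0.3-1%, the 500 asthmatic pregnancies yield 1.5-5 stillbirths. One unclassified death is then at least 1/5 = 20% of the expected count. This is the effect if such a death occurs; its probability is not known.

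**Loss to follow-up.** Section 8.9 cites loss below 5%. At the 5% limit the exclusions are 0.05 × 200 = 10 exposed and 0.05 × 300 = 15 asthmatic comparison pregnancies. A woman interviewed at 32-34 weeks who then withdraws loses 12-14 observed weeks beyond week 20. Lost women bring no observed stillbirth, so exclusion removes only event-free time and raises the rate. If their time at risk averages no more than that of the women retained, the rise is at most 0.05/0.95 = 5.3% in a cohort with 5% loss. Equal loss with similar timing roughly cancels in the ratio; unequal loss does not.

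**First dose after enrolment.** The assumptions are no true effect, enrolment at week 8, follow-up to week 20, constant hazard λ = 0.01 per week, and a share f due to start uniformly over weeks 9-20 if still pregnant. Let u be weeks from enrolment to first dose.
- Exposed events per woman: E = (1 - f)(1 - e^(-12λ)) + f × mean(e^(-λu) - e^(-12λ)) = 0.11308(1 - f) + 0.05062f
- Pre-dose time counted as exposed, times λ: D = f × λ × mean(u e^(-λu)) = 0.0600f
- Apparent rate ratio: E/(E + D)

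| f | E | D | Ratio |
|---|---|---|---|
| 1% | 0.11246 | 0.00060 | 0.995 |
| 2% | 0.11183 | 0.00120 | 0.989 |
| 5% | 0.10996 | 0.00300 | 0.973 |
| 10% | 0.10683 | 0.00600 | 0.947 |
| 20% | 0.10059 | 0.01200 | 0.893 |

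Simulations with other assumed rates and entry times for spontaneous abortion, preterm delivery and stillbirth also gave about 0.95 at 10%. Starting exposed time at first dose returned about 1.00, and so did f = 0.

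For comparison, 200 v 300 women under this hazard have 22.6 and 33.9 expected events. The 95% upper limit around a ratio of 1 is exp(1.96 × √(1/22.6 + 1/33.9)) = 1.70.

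**The case against.** A reader might infer from Table 4 that all pregnancy time before the first dose counts as exposed, so that immortal time affects the whole mepolizumab cohort. The documents do not support that. The Table 4 sentence is an eligibility window and does not say when exposed time starts. Risk time begins at enrolment, and section 8.7.1 names left truncation for spontaneous abortion, so a woman dosed before enrolling contributes no pre-dose time. Cohort 1 entry is worded as exposure already past. Section 8.5 expects nearly every exposed participant to have a first-trimester dose and typically to enrol once pregnancy is recognised. Section 8.9 does say "It is unknown what the distribution of timing of exposure will be in the mepolizumab-exposed cohort", but goes on to note that exposure in the comparable omalizumab registry fell mainly in the first trimester.

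A reader might also infer that a Cohort 2 woman who later starts mepolizumab is moved to Cohort 1 and removed from the comparator. No section states such a rule; the protocol is silent on her.

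Time-dependent coding could properly be set in the Data Analysis Plan, which is not shown, and sampling error far exceeds the bias at plausible shares. These objections stand and reduce the exposure point to a gap for a small group.

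Against the two main points, expected loss is low, no differential loss has been shown, and the boundary gap is one day if age is computed from dates. That limits their size but does not remove them. Both are rules stated in the protocol, not details left to a later plan.

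**Conclusion.** Two rules need correcting. The endpoint definitions omit 20 weeks 0 days, and the stillbirth denominator conflicts both with the method assigned to it and with the spontaneous-abortion row. The expected effect is small. The gap is one day unless completed weeks are used, which the protocol does not settle: the forms use dates and week-plus-day notation, but one delivery field is in weeks. Exclusion costs at most about 5% of pregnancies per cohort at the stated loss, and matters for the ratio mainly if loss or its timing differs by cohort. The stillbirth rate used for scale is an assumption.

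The exposure point is secondary. It concerns only women first dosed after enrolment, whose share the protocol does not give. The ratios of about 0.99 and 0.95 rest on assumed shares of 1-2% and 10%. The same Table 4 sentence appears for small for gestational age, but that outcome is not analysed as time to event.

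None of this touches the primary endpoint of major birth defects in live births, or Table 3.

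**What to change.** 1. Section 8.3.2: define stillbirth as fetal death at or after 20 weeks 0 days, and state that gestational age at loss is held in days.
2. Table 4, Still Birth row: keep enrolled pregnancies with any follow-up after enrolment, and censor those lost or withdrawn at last contact. Report loss by cohort.
3. Section 8.7.1 or the Data Analysis Plan, for spontaneous abortion, preterm delivery and stillbirth: start exposed time at the later of enrolment and first dose, using a time-dependent exposure in the Cox models. State how the time of a Cohort 2 woman who starts mepolizumab is allocated; counting it as unexposed up to the first dose is consistent with this. Report how many women were first dosed after enrolment.

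The cost is wording and coding. Dose dates, enrolment dates and interview dates are already on the Annex 2 forms, so no new data collection or change in sample size is needed.
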